5.1.3 Demographic and Other Baseline Characteristics

Demographic variables and other baseline characteristics will be summarized by phase and treatment based on Safety Analysis Set. The variables to be summarized will include (but will not be limited to):

- Age (continuous variable)
- Age group (< 65 vs. \geq 65)
- Gender
- Race

•

- Ethnicity
- Geographic Region (US, Europe, Japan)
- Body mass index (BMI), calculated as weight (kg) / (height (m))²
- ECOG performance status

5.1.4 Baseline Disease Characteristics

Baseline PTCL characteristics will be summarized by phase and treatment based on Safety Analysis Set. The variables to be summarized will include (but will not be limited to):

- Time since initial diagnosis
- Histopathological diagnosis
- Time since most recent relapse/refractory diagnosis
- Initial stage and Ann Arbor staging
- Current stage and Ann Arbor staging
 - Prior anticancer therapy, prior radiotherapy, and prior surgery
 - Number of regimens continuous and categorical (1, 2, 3+)
 - Time since most recent treatment
 - Best response to any prior treatment
 - Best response to most recent prior treatment
 - Duration of response to most recent prior treatment
 - Prior CHOP (Yes, No)
 - Prior CHOEP (Yes, No)
 - Prior CHOP or CHOEP (Yes, No)
 - Prior Salvage Chemotherapy after CHOP or CHOEP (Yes, No)
 - Prior BV-CHP (Yes, No)
 - Prior stem cell therapy (Yes, No)

5.1.5 Medical History

Medical history will be summarized by phase and treatment based on the Safety Analysis Set.

Medical history will be summarized by system organ class (SOC) and preferred term (PT) using the number and percentage of patients who had at least one occurrence of an SOC or PT. The summary will be sorted alphabetically by SOC and by decreasing frequency of PT within an SOC.

5.1.6 **Prior and Concomitant Medications**

Medications will be considered as prior if they stopped before the date of first dose of study drug.

Medications will be considered concomitant if they were taken at any time between the first dose of study drug and 30 days after the last dose of study drug, inclusive. If the start date or end date of a medication is completely or partially missing refer to Section 4.3.2 for the algorithm to determine whether a medication is concomitant.

Prior medications and concomitant medications will be summarized separately. Both summaries will be based on the Safety Analysis Set. Prior anti-cancer systemic therapies will be summarized separately from other prior medications.

Medications will be summarized by phase and treatment by anatomical therapeutic chemical (ATC) level 1, ATC level 2, and preferred drug name for each cohort. The summary will be sorted by decreasing frequency in ATC level 1, ATC level 2 and preferred drug name. A patient taking the same drug multiple times will be counted once.

A listing will be provided for all non-study medications taken on the study. An identifier will be provided to show if a medication is prior to concomitant. Medications that started more than 30 days after the last dose of study drug will be identified as post-treatment.

Additional groupings of medications will be defined to identify medications administered to treat adverse events specific to the duvelisib risk profile.

5.1.7 Exposure to Study Drug

Extent of exposure will be summarized by phase and treatment based on the Safety Analysis Set.

Extent of exposure will be summarized for the following variables by cycle and overall:

- Duration (weeks): (date of last dose date of first dose + 1) divided by 7.
- Treatment duration categories (\leq 56 days, 57 112 days, > 112 days)
- Number of cycles started (continuous and categorical)
- Cumulative dose received (mg) (continuous and categorical by quartiles)
- Cumulative dose received (mg) during Cycles 1 and 2 (continuous and categorical by quartiles)
- Dose Intensity (mg/day) defined as total actual dose divided by duration in days
- Relative dose intensity, defined as 100% x (total dose received)/(planned cumulative dose for the duration of treatment)
- Average daily dose received (mg)
- Number and percentage of patients within Dose Optimization Cohort 1 with dose escalations to 50mg BID and 75mg BID
- Number and percentage of patients with a dose reduction
- Number and percentage of patients with a dose hold
- Number and percentage of patients for whom study drug was discontinued

Cumulative dose quartiles will be based on doses for all patients in the safety analysis set with all treatment groups combined.

For relative dose intensity, planned dose is defined as follows:

- Dose Optimization Cohort 1: 25 mg × 2 × total days treated at starting dose. For subjects whose assigned dose escalated due to SD at the end of Cycles 1 and 3 as described in the CSP, raise the planned dose accordingly.
- Dose Optimization Cohort 2: 75 mg \times 2 \times total days treated

Expansion Phase: 75 mg × 2 × (28 × 2) + 25 mg × 2 × (total days treated – (28×2)) if patient receives > 2 cycles of treatment *or* 75 mg × 2 × total days treated if patient received < 2 cycles of treatment.

Where total days treated = last dose date - first dose date + 1.

A by-patient listing will be presented for exposure to study drug. A separate listing of dose modifications will be provided for patients who received at least one dose modification.

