#### 9.1.1. Dose Optimization Phase

In the Dose Optimization Phase, the duvelisib dose schedule is dependent on the cohort allocation, as follows:

- Cohort 1: Duvelisib PO BID at a starting dose of 25 mg, with potential escalation on a per-patient basis to 50 mg and then 75 mg, based on the patient's response to and tolerance of therapy, in 28-day cycles
- Cohort 2: Duvelisib 75 mg PO BID, administered in 28-day cycles

In Cohort 1, all patients will receive duvelisib at a starting dose of 25 mg PO BID (Level 1), with potential escalation to 50 mg PO BID (Level 2), and then to 75 mg PO BID (Level 3). The duvelisib dose will be escalated on a per-patient basis in 25-mg increments as follows.

After completion of Cycle 1 and every 2 cycles thereafter:

- Patients with CR or PR will have their duvelisib dose maintained at the current dose level
- Patients with SD will have the duvelisib dose increased to the next level until the next response assessment or development of PD or intolerance

Patients with PD, who are not tolerating therapy, or not otherwise suitable to continue receiving therapy, will have duvelisib discontinued

In no case will the duvelisib dose be increased to a level > 75 mg BID (total daily dose 150 mg).

All patients in the Dose Optimization Phase will receive duvelisib until development of PD or unacceptable toxicity, as determined by the Investigator. Note that for the purposes of patient management during the conduct of the study, the Investigator's assessment of disease response will be used. Dose Optimization Phase patients will complete treatment as defined for their cohort.

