#### 9.1.2. Expansion Phase

The duvelisib dose in the Expansion Phase will be:

Duvelisib PO at 75 mg BID for the first 2 cycles (cycle = 28 days) until the first response assessment (See Table 4). Then, dose will be reduced to 25 mg BID and administered in 28-day cycles.

If a subsequent assessment demonstrates progression and the patient did not require a dose modification due to toxicity, the dose can be re-escalated to 75 mg BID with a confirmatory scan after approximately 4 weeks of therapy. If the patient has progressive disease at the confirmatory scan, then the patient should be discontinued. Patients that re-escalate to 75 mg BID may remain at this dose level until the need for dose modification or the criteria for discontinuation is met.

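### The SAP's planned dose for relative dose intensity has no term for permitted Expansion re-escalation, so fully compliant re-escalated patients, and only those in that phase, score above 100%

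*SAP*

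**What the plan says.** SAP 5.1.7 gives the measure as "Relative dose intensity, defined as 100% x (total dose received)/(planned cumulative dose for the duration of treatment"). It heads the list of exposure variables with "Extent of exposure will be summarized for the following variables by cycle and overall". The planned dose is then set by phase and cohort:

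- **Expansion, more than 2 cycles:** 75 mg BID for 56 days, plus "25 mg × 2 × (total days treated – (28×2)) if patient receives > 2 cycles of treatment".
- **Expansion, shorter treatment:** 75 mg × 2 × "total days treated if patient received < 2 cycles of treatment".
- **Cohort 1:** 25 mg BID, with an upward adjustment: "For subjects whose assigned dose escalated due to SD at the end of Cycles 1 and 3", the planned dose is to go up to match.
- **Time base:** "Where total days treated = last dose date - first dose date + 1".

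On Expansion dosing, Protocol 9.1.2 says that, after progression in a patient who needed no dose modification for toxicity, "the dose can be re-escalated to 75 mg BID with a confirmatory scan after approximately 4 weeks of therapy". It sets no fixed end to the re-escalated period, unless the confirmatory scan shows progression. SAP 3.1.2 also mentions re-escalation.

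For Cohort 1, Protocol 9.1.1 places the dose reviews "After completion of Cycle 1 and every 2 cycles thereafter".

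**The concern.** The count of treated days runs from first to last dose, so it includes re-escalated days. On those days an adherent patient takes 150 mg, while the formula plans 50 mg. Relative dose intensity (RDI) should show how much of the assigned treatment was delivered. Here it would also pick up a dose increase that the protocol allows.

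Two consequences follow. First, RDI means different things in the two phases: Cohort 1 is measured against a planned dose that follows escalation, and Expansion is not. Second, within the RDI variable itself, values above 100% offset genuine shortfalls, both within a patient and in a group mean. SAP 5.1.7 counts escalated patients only for Cohort 1, so the summary tables would not show how many Expansion values above 100% come from re-escalation.

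**Working it through.** The documents state no RDI value, so there is no figure to reproduce. The check applies the SAP formula to patients who take every assigned dose on the nominal schedule.

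**Inputs.** From SAP 5.1.7 and Protocol 9.1.2: 75 mg BID = 150 mg/day for 56 days, then 25 mg BID = 50 mg/day, with re-escalation at 150 mg/day. Assumed: *a* days at 25 mg BID before re-escalation and *b* days re-escalated. In Protocol Table 4, 56 days is the shortest nominal gap between the Cycle 3 scan and the next scheduled one; 336 days is an arbitrary long case.

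**Formulas.**

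- Received = 8,400 + 50*a* + 150*b* mg
- Planned (SAP) = 8,400 + 50(*a* + *b*) mg
- RDI = 100 × received / planned

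**Baseline check.** With no re-escalation and 168 days treated, 14,000 / 14,000 = 100.0%. The formula is right for everyone on the base schedule.

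| *a* (days) | *b* (days) | Received (mg) | Planned (mg) | RDI |
|---|---|---|---|---|
| 56 | 7 | 12,250 | 11,550 | 106.1% |
| 56 | 28 | 15,400 | 12,600 | 122.2% |
| 56 | 56 | 19,600 | 14,000 | 140.0% |
| 56 | 112 | 28,000 | 16,800 | 166.7% |
| 336 | 7 | 26,250 | 25,550 | 102.7% |
| 336 | 28 | 29,400 | 26,600 | 110.5% |
| 336 | 112 | 42,000 | 30,800 | 136.4% |

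If the planned dose follows the assigned dose day by day, every row becomes 100%.

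**By cycle.** The SAP gives no separate by-cycle formula. Applying the 25 mg BID term to a cycle spent wholly at the re-escalated dose gives (150 × 28) / (50 × 28) = 4,200 / 1,400 = 300%.

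**Offsetting within a patient.** Take *a* = 56 and *b* = 56, with 28 of the re-escalated days held and dosing then resumed. Received = 19,600 − 4,200 = 15,400 mg. Against the SAP plan this is 15,400 / 14,000 = 110%. Against the assigned dose it is 15,400 / 19,600 = 79%.

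**Effect on a group mean.** The number re-escalated is not given. If 10% were re-escalated for 28 days and all other patients scored 100%, the mean would rise by 0.10 × 10.5 = 1.05 points (*a* = 336) to 0.10 × 22.2 = 2.2 points (*a* = 56). Longer re-escalation or a larger share would raise it further.

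**Cohort 1.** SD at the end of Cycles 1 and 3 is covered: 23,800 / 23,800 = 100% over seven cycles. The literal wording misses an escalation at the end of Cycle 5 or later. Take SD at Cycle 1, PR at Cycle 3, SD at Cycle 5, then two more cycles:

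- Received = 50 × 28 + 100 × 112 + 150 × 56 = 21,000 mg
- Planned = 50 × 28 + 100 × 168 = 18,200 mg
- RDI = 115.4%

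**Exactly 2 cycles.** The wording leaves this case undefined, but both branches give 150 × 56 = 8,400 mg at day 56.

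**The case against.** The best defence is that RDI may be measured against the base regimen. Cohort 1 escalation for SD is directed, whereas Expansion re-escalation is optional, so a value above 100% would show that more drug was given than the base regimen calls for. As a stated convention this would be coherent. The SAP does not state it, however, and the same list adjusts the planned dose for Cohort 1 escalation.

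The objections to a broader claim do stand:

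- **A reader might infer that compliant patients in general exceed 100%.** They do not. Re-escalation requires progression after the reduction and no earlier dose modification for toxicity, and patients with progression at the confirmatory scan stop. Other compliant Expansion patients score 100%.
- **A reader might infer that holds and reductions would go unseen.** SAP 5.1.7 reports the number and percentage of patients with each, lists dose modifications by patient, and also gives cumulative dose, dose intensity in mg/day and average daily dose. SAP 4.1 adds medians and quartiles. The masking is confined to the RDI variable.
- **A reader might infer that all Cohort 1 escalation from Cycle 3 on is missed.** The SAP names the end of Cycle 3. A patient with SD at Cycles 1 and 3 is already at the 75 mg BID ceiling, so a missed escalation needs a less direct path, such as PR followed by SD. The SAP's cross-reference to the protocol also suggests that the intent was to follow the assigned dose.
- **A reader might want the '< 2 cycles' condition changed to '≤ 2 cycles'.** That edit changes no number.

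**Conclusion.** The point holds for Expansion patients who are re-escalated. Their RDI is overstated even with perfect adherence, and the direction is always upward. The excess ranges from a few points for a week of re-escalation to about two thirds for 112 days after a short spell at 25 mg BID. It depends on durations that the documents do not give, and the effect on group summaries depends on an unknown number of patients.

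The consequence is limited. RDI is one descriptive exposure variable among several. No efficacy analysis uses it, and the adverse-event subgroups in SAP 5.3.1.2 use cumulative dose instead. What needs correcting is that one measure has two meanings in the same section and does not match the dosing sections it is meant to reflect. The Cohort 1 wording is a minor matter of the same kind. None of this bears on which dose rule is right.

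**What to change.** In SAP 5.1.7, define the planned dose in both phases as the sum, over days from first to last dose, of the protocol-assigned dose on each day. Expansion days after a documented re-escalation then count at the assigned level. Report the number and percentage of Expansion patients re-escalated, as the SAP already does for Cohort 1 escalations. As a minor edit, replace the reference to the end of Cycles 1 and 3 with any scheduled review, to match Protocol 9.1.1.

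The cost is one definition, one added table row and modest programming. It assumes that the date and level of each assigned dose change are in the database. The eCRF specification is not among the documents, but the planned by-patient listing of dose modifications suggests that they are.

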5.2 Efficacy Analyses

For the Dose Optimization Phase, all primary and secondary efficacy analyses will be performed using the Dose Optimization Efficacy Set and will be based on the Investigator's determination of response, with the IRC's determination of response used for supportive efficacy analyses. Analysis of the Expansion Phase primary and secondary efficacy analyses will be performed using the mITT Analysis Set and will be based on the IRC's determination of response, with the Investigator's determination of response used for supportive efficacy analyses. Response will not require confirmation by a second assessment.

Listings of efficacy endpoints will be provided. The listing of best overall response (including unknown response) will include histological type, reason for treatment discontinuation, flag for death, and time to death.

5.2.1 Analyses of Primary Endpoint

5.2.1.1 Primary Analysis of ORR/BOR

ORR and BOR as determined by both the IRC and the Investigator will be presented along with 2-sided confidence intervals using normal approximation.

Swimmer's plots will be produced with time on study as the x-axis and patient ID along the y-axis. Different symbols representing the study day of each IRC response (CR, PR, SD, PD, NED), end of treatment reason (PD, AE, death, transplant, other), and end of study reason (death, other) will be plotted for each patient. Patients will be grouped by best overall response.

5.2.1.2 Subgroup Analysis of ORR/BOR

Subgroup analysis of ORR by subject demographics and baseline disease characteristics will be tabulated using response determined by the IRC in the mITT Analysis Set. BOR will be analyzed by select subgroups. Potential subgroups to be included are described in Section 4.5.

5.2.1.3 ORR/BOR by prognostic factors

The primary analysis will be repeated by the prognostic factors described in section 4.5.2. A forest plot will be presented for the expansion phase and for all patients combined plotting ORR with 95% CI for each prognostic factor and component.

5.2.2 Analyses of Secondary and Exploratory Efficacy Endpoints

5.2.2.1 Duration of Response

Duration of response will be analyzed both for patients with ORR (CR or PR) and for patients with CR.

- Main DOR Analysis: DOR will only be calculated for those patients with a CR or PR from time to first response to PD or death (if death occurs prior to PD). Patients who withdraw from the study for any reason prior to PD and patients who have ongoing response at the time of the data cut will be censored at the date of their last response assessment.
- Duration of complete response (DOCR): DOCR is calculated from the time of first CR and only includes patients who had at least one CR response. It is otherwise defined the same as the Main DOR endpoint.

Estimates of the 25th percentile, median, and 75th percentiles will be for each of these DOR endpoints will be presented using the Kaplan-Meier method. A 2-sided 95% confidence interval for median DOR will be provided by using the Brookmeyer-Crowley method. Kaplan-Meier plots will be provided.

In addition, the number and percent of patients with duration of response of at least 3 months, 6 months and 12 months will be tabulated.

A summary of time to first response will also be presented in patients who achieved CR or PR and in patients who achieved CR.

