#### Table 4: Expansion Phase Disease Response and Follow-up Assessments

				Cycle	/ Day		-			
			Cycle 1		Сус	le 3	Cycle 5 and then every 2 cycles 	End of Treatment (EOT) 	PD Follow- up 	Survival Follow- up 
Procedure 	Screening D-30 to -1	D1	D8 ± 3	D15 ± 3	D1 ± 3	D15 ± 3	D1 ± 4	≤7 d from last dose	Q2M (± 1M)	Q3M (± 1M)
PET-CT or CT or MRI 	X7				X 		X	X	Х	
ECOG performance status	X						X	X	Х	
Survival status										X

Abbreviations: C = cycle; CT = d = day; D = Study Day; ECOG = Eastern Cooperative Oncology Group; EOT = End-of-Treatment; FDG = fluorodeoxyglucose; IRC = independent review committee; M = month; MRI = magnetic resonance imaging; PD = progressive disease; PET = positron emission tomography; PTCL = peripheral T-cell lymphoma; Q2M = every 2 months.

- 1. See Section 6.11 for additional information on disease response assessments.
- 2. Additional visits may be scheduled / procedures may be performed at the Investigator's discretion, as clinically indicated.
- 3. The EOT visit is to be performed within 7 days after the last study drug dose.
- 4. Patients who discontinue treatment from duvelisib for reasons other than PD are to have disease response assessments performed Q2M until the development of PD, as determined by the Investigator, death, or initiation of alternate anti-cancer therapy.
- 5. After development of PD, as determined by the Investigator, patients are to be followed Q3M for survival until closure of the study by the Sponsor; this follow-up may be conducted via telephone.
- 6. PET-CT is the preferred method of assessment. The modality chosen to evaluate response in each individual patient should be the same throughout the duration of the study. PET images are to be assessed using the 5-point scale (5PS). At each scheduled timepoint, the Investigator will be asked to provide a PET-CT-based response, based on the Lugano (Cheson et al. 2014) response criteria. Images will be centrally stored and read, with disease response determined by the IRC using the central image assessments.

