# **10.3.** Reporting of Adverse Events and Serious Adverse Events

The AE reporting period begins from the time that the patient signs the ICF through and including 30 calendar days after the last study drug dose. All treatment-related AEs/SAEs should be followed until resolution or stabilization. Any SAE occurring after the reporting period must be promptly reported if a causal relationship to the investigational drug is suspected. If the patient begins a new anticancer therapy, the safety reporting period ends at the time the new treatment is started, however, death must always be reported if it occurs during the AE reporting period irrespective of intervening treatment.

Elective or previously scheduled hospitalizations for pre-existing conditions that have not worsened after initiation of treatment should not be classified as SAEs. For example, an admission for a previously scheduled ventral hernia repair would not be classified as an SAE.

All AEs should be recorded individually unless, in the opinion of the Investigator or designated physician, the AEs constitute components of a recognized condition, disease, or syndrome. In the latter case, the condition, disease, or syndrome should be reported rather than each individual sign or symptom. If a constellation of signs and/or symptoms cannot be medically characterized as a single diagnosis or syndrome at the time of reporting, each individual event should be recorded as an AE or SAE as appropriate on the relevant form(s) (SAE Report Form and/or AE eCRF). If a diagnosis is subsequently established, it should be reported as follow-up information is available. If a diagnosis is determined subsequent to the reporting of the constellation of symptoms, the signs/symptoms should be updated to reflect the diagnosis.

Each AE is to be evaluated for duration, severity, seriousness, and causal relationship to the investigational drug. The action taken with study drug and the outcome must also be recorded.

All SAEs, regardless of relationship to the study treatment, must be reported immediately to the Sponsor and Contract Research Organization (CRO) pharmacovigilance group, with the timeframe not to exceed 24 hours of the Investigator becoming aware of the event. Initial SAE

notification should be made by e-mailing or faxing the SAE report form to the e-mail or fax number provided on the SAE report form.

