2.5.2 Expansion Phase

- TEAEs and changes in laboratory values
- DOR, for those patients with CR or PR, defined as the time from the first documentation of response to the first documentation of PD, as determined by the IRC, or death due to any cause
- PFS, defined as the time from the first dose of study treatment to the first documentation of PD, as determined by the IRC, or death from any cause
- DCR, defined as $CR + PR + SD \ge 8$ weeks, calculated using IRC-determined responses
- OS and deaths
- PK parameters of duvelisib and its metabolites

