5.2.2.3 Analysis of PFS

For the PFS analyses, censoring of PFS will be performed as detailed in Table 2. Note that progression may be documented based on scheduled or unscheduled disease status assessment, and that unscheduled disease status assessments will be included in calculating the gap between adequate disease status assessments.

PFS will be estimated for each cohort using the Kaplan-Meier method. PFS will be plotted by using the Kaplan-Meier method. Number of patients with events, type of events (progression or death), number of patients censored, number of patients for each reason of censoring, Kaplan-Meier estimates and 95% confidence intervals for the 25th percentile, median, and 75th percentile for PFS will be presented. A 2-sided 95% confidence interval for median PFS will be provided by using the Brookmeyer-Crowley method. Probabilities of remaining alive and progression free at selected time points may also be presented.

PFS analysis will be repeated for the subset of enrolled Japanese patients and for each of the prognostic factors described in section 4.5.2

Situation	Date of Event or Censoring	Outcome
No adequate baseline disease status assessment	Date of randomization + 1 day	Censored
No adequate post-baseline disease status assessment unless death occurs prior to first scheduled post-baseline assessment	Date of randomization + 1 day	Censored

Table 2: Primary PFS Censoring/Event Rule

No documented progression or death	Date of last adequate disease status assessment	Censored
Documented progression with ≤1 missing scheduled disease status assessment before progression	Date of the earliest assessment that results in a finding of unequivocal progression	Event
Death before progression being documented with ≤1 missing scheduled disease status assessment before death	Date of death	Event
Documented progression or death following a gap between adequate disease status assessments equivalent to 2 missed visits	Date of last adequate disease status assessment before the gap	Censored
New anticancer treatment or procedure started before documented progression or death.	Date of last adequate disease status assessment prior to start of new anticancer therapy	Censored

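### DOR has no rule for responders whose scans stop without IRC progression: a recorded later death is an event, survival is most naturally censoring at the last scan, and Table 2's remedies cover PFS only

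*SAP*

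**What the plan says.** **DOR rule.** SAP 5.2.2.1 runs DOR from first response to PD, or to death if death comes first. It names two censoring cases, both dated at the last response assessment. One is withdrawal from the study before PD. The other is ongoing response: "patients who have ongoing response at the time of the data cut will be censored at the date of their last response assessment". For complete responders, the matching measure (DOCR) starts at first CR and otherwise copies this rule. The section adds that "the number and percent of patients with duration of response of at least 3 months, 6 months and 12 months will be tabulated". It mentions neither new therapy nor missed assessments, and it does not refer to Table 2.

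**PFS rule.** SAP 5.2.2.3 applies Table 2 to PFS. Two of its rows censor at the last adequate assessment beforehand: "New anticancer treatment or procedure started before documented progression or death" and "Documented progression or death following a gap between adequate disease status assessments equivalent to 2 missed visits".

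**Whose progression counts.** For the Expansion Phase, SAP 2.5.2 ends DOR at "the first documentation of PD, as determined by the IRC, or death due to any cause".

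**Follow-up.** Under Protocol Table 4, footnote 4, patients off drug without PD are scanned "until the development of PD, as determined by the Investigator, death, or initiation of alternate anti-cancer therapy". Footnote 5 adds: "After development of PD, as determined by the Investigator, patients are to be followed Q3M for survival". Once a patient starts new anticancer therapy, Protocol 10.3 closes the safety reporting period, except that "death must always be reported if it occurs during the AE reporting period irrespective of intervening treatment".

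Protocol 11.9 leaves censoring rules to the SAP, so nothing else fills the gap.

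**The concern.** Two kinds of responder can lose their scans without IRC progression.

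- **Route A: new therapy, such as transplant, without progression.** Scheduled scans end. No survival contact is scheduled, because survival follow-up is written only for the time after Investigator PD. Some later deaths may still reach the database, since SAP 5.2.2.4 analyses OS and 5.3.8 summarises deaths before progression.
- **Route B: Investigator PD that the IRC does not call, with duvelisib stopped.** No further scans are scheduled, but three-monthly survival follow-up begins, so the protocol itself collects the death. Protocol 7.1 treats documented PD as study completion, so the withdrawal rule does not clearly apply. Patients who stay on drug after Investigator PD are outside this route.

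In both routes a recorded death is a DOR event however long after the last scan it occurs. A living patient fits neither censoring case exactly, but is most naturally censored at the last scan. Observed DOR time then depends on whether the patient later dies. DOR is the main support for ORR in a single-arm trial, and durability also enters the futility review (SAP 3.5).

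**Working it through.** The plan gives no DOR assumption, event count or precision, so there is no stated figure to reproduce.

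**1. One patient under both rules.** First response at month 2 from first dose; last scan and new therapy at month 4; no IRC PD; not recorded as withdrawn.

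| Later course | DOR, SAP 5.2.2.1 | PFS, Table 2 |
|---|---|---|
| Death recorded at month 16 | event at 16 − 2 = 14 months | censored at month 4 |
| Alive at the data cut | censored at 4 − 2 = 2 months (natural reading) | censored at month 4 |

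The DOR clock starts two months after the PFS clock, yet DOR (14 months) exceeds PFS (4 months). The patient who died enters the 12-month row with no scan after month 4.

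**2. Size, on assumed inputs.** Responders: 40% (the alternative ORR) × 130 = 52. All else is assumed: median DOR 4, 7 or 10 months; 15% of underlying events are deaths; data cut 6-30 months after response; 8-week scans. Differences are the SAP rule minus the Table 2 rows.

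| Setting | Patients at ≥6 months | Patients at ≥12 months | KM at 12 months, points |
|---|---|---|---|
| A: new therapy in 5-30%, no later deaths captured | 0 | 0 | 0 |
| A: 30% of later deaths captured | +0.1 to +1.6 | +0.1 to +0.7 | see next row |
| A: all later deaths captured | +0.4 to +5.2 | +0.2 to +2.3 | −3.8 to +1.3 (all A settings) |
| B: 5-20% of responders, deaths captured | +0.4 to +3.0 | +0.2 to +1.5 | −4.4 to +0.8 |
| Two missed scans, then PD or death, in 5-10% | +0.3 to +0.8 | about +0.1 | −1.0 to −0.3 |

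Median survival after the stop was 12 or 24 months in A. In B it was 6 or 8.4 months, borrowed from the OS figures in Protocol 1.1 and 1.2.

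**3. Are the crude counts inflated?** These differences measure distance from Table 2, not from the truth. Take median 7 months, 30% new therapy, 12-month survival afterwards and full capture.

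- True 12-month share. Six 8-week intervals are about 11.0 months, so PD arising by then is found before month 12. The share is 0.85 × 0.5^(11.0/7) + 0.15 × 0.5^(12/7) = 0.85 × 0.336 + 0.15 × 0.305 = 33%.
- Crude 12-month share: 20.4% under the SAP rule, 16.7% under Table 2, and 23.7% if no scans stopped.
- Kaplan-Meier at 12 months: 0.309 under the SAP rule, 0.326 under Table 2.

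Most of the crude shortfall comes from the data cut. With cuts spread evenly over 6-30 months, only (30 − 12)/(30 − 6) = 75% of responders can be seen to reach 12 months, and 0.75 × 33% is about 25%. Crude counts treat the rest as failures under either rule.

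**4. A harsher illustration.** Median DOR 8 months; scans stop in 10-40%, always before the underlying progression; survival afterwards 4-16 months; all deaths captured. Twelve-month Kaplan-Meier DOR is 0.37-0.47 under the SAP rule and 0.40-0.50 with Table 2 carried over. Setting by setting, the gap runs from 0 (0.40 and 0.40) to 12 points (0.38 against 0.50, at 40% stopping and 4-month survival). The median is 9.2-11.0 months under either rule. The true 12-month value is 0.5^(11.0/8) = 0.39, so when stopping is linked to coming progression, Table 2 censoring can overstate DOR.

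**The case against.** **It may be a choice of estimand.** Protocol 3.2.2 and SAP 2.5.2 define DOR to PD or death from any cause, and counting events regardless of new therapy is a recognised approach. That stands in part. But the approach needs progression to be observed after new therapy, and scheduled scans stop then, leaving mainly death observable. The SAP does not state this intention and does the opposite for PFS.

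**The written rule is usually the more conservative one for Kaplan-Meier.** This stands. The larger shifts lower DOR, and aligning with Table 2 would usually raise the estimate.

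**The effect rests on stacked conditions.** This also stands. Route A vanishes if later deaths are not captured. The difference can disappear if a site records withdrawal under the open category in Protocol 8.2, because 5.2.2.1 then censors. Route B needs the IRC and the Investigator to disagree, and the IRC also reviews clinical data under a charter not available here (Protocol 4.1.3).

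**Much is visible elsewhere.** Swimmer's plots show IRC response days and end-of-treatment reasons, including transplant. The response listing gives time to death. This helps a reader trace individual patients but does not settle the estimate.

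**A tempting stronger reading** is that the landmark table flatters the drug. The documents give no basis for that, and the check in step 3 points the other way. In 18 Route A settings with full capture, the SAP crude count at 6 and 12 months never exceeded the count expected with no new therapy. Nor has every added patient died: after two missed scans, patients with late PD are added too.

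**Conclusion.** The concern holds as a defect in the DOR rule. Followed as written, it makes a responder's observed duration depend on later death once scans stop, and it can give a DOR longer than the same patient's PFS.

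The size cannot be fixed from the documents, which give no number of responders starting new therapy, no rate of IRC/Investigator disagreement and no rate of missed scans. In the main simulation the 12-month Kaplan-Meier shift is about 0 to 4 points, mostly lowering DOR. Only heavier assumed stopping with short survival takes it to 12. Where later deaths are not captured, or withdrawal is recorded, there is no effect.

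Overall inflation of the 3-, 6- and 12-month counts is not shown. They understate durability under either rule, because responders censored early count as not reaching the landmark. What remains is narrower: some patients counted as reaching a landmark have no scan showing response that late. The primary endpoint, ORR, is untouched. The point deserves correction, with medium confidence about its practical weight.

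**What to change.** In SAP 5.2.2.1:

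1. Report 3-, 6- and 12-month DOR and DOCR as Kaplan-Meier probabilities with 95% confidence intervals. Keep the crude counts as supplementary only. In the step 3 example the Kaplan-Meier values were 31-33% against a true 33%, where crude shares were 17-20%.
2. Apply the Table 2 rows for new anticancer treatment or procedure and for a gap of two missed visits to DOR and DOCR, with the clock starting at first response (first CR for DOCR). Censor an IRC responder whose scans stop after Investigator PD without IRC PD at the last adequate assessment. The Table 2 rows dated from randomization need not carry over.
3. Add a sensitivity analysis that counts PD or death regardless of new therapy or missed visits, because censoring at transplant or Investigator PD may be informative, as step 4 shows.

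The data appear to be collected already: SAP Table 1 provides for coding of post-treatment systemic therapy, and 4.5.2 uses post-baseline transplant as a factor.

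The cost is SAP wording and programming. DOR will have more censoring and fewer events, and the crude counts will fall. In the step 4 illustration the share of responders with an event drops from 71-85% to 50-76%. N and the stated power do not change.
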